## 6.ELIGIBILITY

This is a single-center study. Twenty RA patients will be recruited over a planned recruitment period of 24 months, and randomized. The target population consists of patients who are deemed methotrexate-inadequate responders by their treating rheumatologist, and who have not recently received a biologic DMARD. Informed consent will be obtained by the Principal Investigator, co-investigator, or Study Coordinator. Study procedures including screening procedures will not begin until signed informed consent has been obtained.

**6.1. Inclusion Criteria:** Subjects who meet all of the following criteria are eligible for enrollment into the study:

- Written informed consent signed by the subject.
- Patients age > 18 years.

- Fulfilling the American College of Rheumatology 2010 classification criteria for RA (60).

- MTX for ≥ 8 weeks at ≥ 15mg weekly or on at least 7.5mg of methotrexate weekly for ≥8 weeks with a documented intolerance of higher MTX doses, and on a stable dose for the previous 4 weeks;
- No recent biologic DMARD treatment defined as prior biologic use other than rituximab in the past 3 months, or rituximab use in the past 6 months.
- If the subject is a woman with childbearing potential, a urine sample will be taken for a pregnancy test. The results of the pregnancy test must be negative.

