#### 2.RATIONALE.

**2.1.** *Preliminary Data.* In a single RHeumatoid arthritis studY of THe Myocardium (RHYTHM study), a total of 119 RA patients without clinical CVD underwent cardiac FDG-PET/CT, with myocardial inflammation assessed qualitatively and quantitatively by visual inspection and by calculation of the standardized-uptake-value (SUV) units. Qualitative myocardial FDG uptake was observed in 39% of the patients (Figure 1). By quantitative assessment, the median

myocardial SUV mean was 1.9 (inter-quartile range [IQR]: 1.5-2.6), and the median SUV max was 3.0 (IQR: 2.1-4.5).

**Figure 1.** Example of diffuse Myocardial F-FDG uptake Scan in an RA patient. Short Axis for a, b and c; horizontal axis for d; and vertical long axis for e.

As expected, RA patients with visually detected FDG uptake had higher SUVs by quantitative assessment than patients without visually detected FDG uptake (median SUV mean of 2.8 [IQR: 2.2-4.9] vs 1.6 [IQR: 1.4-1.9], p <0.0001), and median SUV max of 4.9 [IQR: 3.6-9.4] vs 2.3 [IQR 2.0-2.9], p < 0.0001, respectively). Interestingly, when comparing the degree of myocardial FDG uptake in RA patients on abatacept vs no biologic agents; abatacept treatment (n=8) was associated with a lower SUV mean. This association remained statistically significant with an 18% lower myocardial SUV mean seen after adjusting for disease activity (Clinical Disease Activity Index less vs greater or equal to 10) (beta=-0.36) (Figure 2). No significant difference was seen between myocardial FDG uptake in those on non-biologic DMARDs vs TNF-inhibitors (p=0.69). In addition, higher CDAI and DAS-28 scores, non-Hispanic black race, and body mass index (BMI) were significantly associated with a higher SUV mean. A CDAI ≥10 (moderate/high disease activity) was associated with a 0.31 increase in SUV mean when compared to the group with CDAI in remission or low disease activity (CDAI<10) (beta=0.31, p=0.006). A similar relationship was observed with DAS-28. Non-Hispanic black RA patients had 22% higher SUV mean than non-Hispanic whites (beta=0.31, p=0.006). However, in adjusted analyses, only the CDAI≥10 remained significantly associated with a higher SUV mean.

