2.2. Scientific Premise. This study aims to evaluate the effects of abatacept, a CTLA4-Ig fusion protein that binds CD80/86 (B7-1/B7-2), on subclinical myocarditis in rheumatoid arthritis (RA) through its effect on T cell subpopulations. Animal data showing decreased myocardial inflammation, damage, and mortality, and improved cardiac function with CD40L/B7-1 and CTLA4 blockage, coupled with our preliminary findings of lower myocardial inflammation in RA patients on abatacept vs other DMARDs, suggest that abatacept treatment has potential myocardial benefits. In RA patients, the proportion of peripheral T cell subsets significantly differs from normal controls and include differentiation to memory effector subsets, acquisition of NK receptors, exhaustion markers, and enhanced inflammatory cytokine expression. Importantly, T cell lymphocytic infiltration described in autoimmune myocarditis resulting as a complication of CTLA4 immune checkpoint inhibition, suggests a role for T cell subsets in the pathogenesis of myocarditis in RA with potential differences depending on mechanism of action of the DMARD in use. Studies that investigate the impact of treatment on subclinical myocarditis in RA, a possible contributor to heart failure, while exploring potential underlying mechanisms (i.e. different T cell subpopulations), are needed for a better understanding of their relevance in the pathogenesis of heart failure in RA and survival improvement in these patients with excess risk for cardiovascular death. If our hypothesis is confirmed and treatment with abatacept decreases and/or suppresses or prevents myocardial inflammation in RA, this will have multidisciplinary implications that could lead to changes in the current management of RA patients at high risk for cardiovascular events. Similarly, identification of T cell subpopulations in

RA patients with myocardial FDG uptake will shed light into the underlying cellular mechanisms of myocardial injury and serve to guide the use of therapies that prevent their pathogenicity.

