# 10.SCHEDULE OF ASSESSMENTS

Consent will be obtained at the beginning of the Screening/baseline visit (Visit 1). Patients who meet eligibility criteria and provide informed consent will be considered enrolled and will undergo the additional procedures outlined above in Table 1, including completion of questionnaires, screening laboratory tests including hepatitis B and C screens and tuberculosis screening (if none in the past six months). Subjects found to have active hepatitis or active infection (including tuberculosis) will be excluded. If the required screening blood work was completed by the subject within 2 weeks of the screening visit, these tests do not need to be repeated.

If the subject has been on stable methotrexate or prednisone for the 8 weeks preceding the screening/baseline visit, then safety labs performed during those 8 weeks do not need to be repeated at the screening/baseline visit. If these additional laboratory- and imaging-based eligibility criteria are met and eligibility is confirmed, the cardiac FDG PET/CT scan will be scheduled. For the cardiac FDG PET/CT, the subject will be given instructions for an overnight fast for the purposes of the PET/CT scan. If nothing is found on the FDG PET/CT that would preclude the subject from randomization, the subject will be randomized into the study. The subject will complete additional questionnaires at baseline. An interim/safety visit at 8 weeks will take place, followed by a final visit at week 16. Blood will be drawn at each visit. A repeat cardiac FDG PET-CT scan will be performed at 16 weeks. An additional safety visit at week 20 will be performed to assess potential adverse events.

Treatment drug will be dispensed at the baseline and the week 8 study visits.

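### Baseline FDG uptake plays no part in allocation, and the promised matching of the arms has no mechanism under consecutive alternation

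*Combined protocol and SAP*

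**What the plan says.** - **Entry.** Section 6.1 begins "Subjects who meet all of the following criteria are eligible for enrollment into the study". Its items concern consent, age, classification of RA, methotrexate exposure, recent biologics and pregnancy. Inadequate response appears only in the opening paragraph of section 6, as "patients who are deemed methotrexate-inadequate responders by their treating rheumatologist". Neither 6.1 nor 6.2 has an uptake criterion or a CDAI or DAS28 threshold.
- **Order of events.** Section 10 places the baseline scan before allocation: "If nothing is found on the FDG PET/CT that would preclude the subject from randomization, the subject will be randomized into the study". No other use of the scan at that step is described.
- **Allocation.** Sections 7.2 and 9.2 describe open, consecutive 1:1 alternation with no stratification factor.
- **Matching.** The statistical paragraph of the synopsis and section 12.1 both say that the arms will be matched on age, sex and disease activity. Neither says how, and baseline uptake is not on the list.
- **Analysis.** The synopsis says that the Aim 1 model of change in SUV takes patients' baseline values into account. Section 12.1 describes the same model without that statement.
- **Pilot data (section 2.1).** "Qualitative myocardial FDG uptake was observed in 39% of the patients". Median SUV mean was 2.8 (IQR 2.2 to 4.9) with visible uptake and 1.6 (IQR 1.4 to 1.9) without.

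**The concern.** The primary comparison is of change in SUV between two arms of ten. In the pilot, visible uptake separates patients whose median SUV mean differs by 1.2 units, twice the difference the trial is sized to detect. A handful of uptake-positive patients will therefore largely determine each arm's baseline mean, and nothing in the allocation keeps them evenly spread.

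An arm that starts higher by chance tends to fall further by the second scan, whatever the drug does. If that arm is abatacept, the fall looks like benefit; if it is adalimumab, it hides one. Adjustment for baseline SUV would counter this, but the two descriptions of the Aim 1 model disagree on whether it is made.

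The promised matching does not fill the gap. Alternation assigns by order of arrival and uses no patient characteristic, so any similarity in age, sex or disease activity would be accidental.

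**Working it through.** **Inputs.** Ten per arm, SD 0.5, difference 0.6, 80% power (12.2); two-sided alpha 0.05 (12.1); 39% with visible uptake and medians of 2.8 and 1.6 (2.1).

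**1. The plan's own figure.** With the normal approximation, n per arm = 2 × [0.5 × (1.960 + 0.842) / 0.6]² = 10.9, so 11 against the stated 10. At 10 per arm the power for 0.6 is 76.5%. The difference detectable with 80% power is 0.5 × √(2/10) × 2.802 = 0.626, which rounds to 0.6. The stated size is thus reproduced up to rounding, with 0.6 read as SUV units. Read as a standardised effect, 0.6 would have power of only 26.8%.

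**2. Expected number with visible uptake.** 20 × 0.39 = 7.8, taken as 8.

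**3. Chance of an uneven split.** Assume that enrolment order is unrelated to uptake, so that alternation behaves like a random division into 10 and 10. With exactly 8 positive patients:

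- ways to place them: C(20,8) = 125,970
- ways giving 6:2, 7:1 or 8:0 in either direction: 2 × [C(10,6)·C(10,2) + C(10,7)·C(10,1) + C(10,8)] = 2 × (9,450 + 1,200 + 45) = 21,390
- probability: 21,390 / 125,970 = 0.17

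If the number of positives also varies (two independent binomial arms of 10 at 39%), the arms differ by 3 or more positives with probability 25% and by 4 or more with probability 11%. The figure of 0.17 lies between these because a total of 8 allows only even differences. For assumed prevalences from 30% to 60%, the probability of a gap of 3 or more is 22% to 26%, so the risk depends little on the 39%.

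**4. Size of the baseline gap.** At 6:2 the arms' proportions differ by 0.4. Using medians in place of means, the gap is 0.4 × (2.8 − 1.6) = 0.48 SUV units, and 0.48 / 0.6 = 80% of the planned difference. The positive group is right-skewed (2.1 units from median to upper quartile, 0.6 from lower quartile to median), so the gap in means is more likely above 0.48 than below.

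**5. How much could pass into an unadjusted change.** With no drug effect, equal SDs at both scans and correlation ρ between them, the expected difference in change is (1 − ρ) × 0.48. The documents do not give ρ. The range is 0 (ρ = 1) to 0.48 (ρ = 0), with 0.24 at ρ = 0.5.

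**6. Why uptake rather than disease activity.** Section 2.1 reports that CDAI of 10 or more "was associated with a 0.31 increase in SUV mean when compared to the group with CDAI in remission or low disease activity". The same four-patient imbalance on that factor would move the arms 0.4 × 0.31 = 0.12 apart, a quarter of 0.48.

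**The case against.** The strongest reply is that the plan already deals with this: it promises matching on disease activity, and the synopsis says that baseline uptake enters the Aim 1 analysis. The second part has weight. With baseline SUV as a covariate, most of the bias in step 5 goes. But section 12.1 drops the statement, and the synopsis wording names no covariate, so it could mean only that change is analysed. Adjustment also cannot restore information when one arm has only two positive patients. That matters for Aim 2 as well, whose models are run within each arm.

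Second, the 39% comes from a cohort on mixed treatments. This trial enrols methotrexate-inadequate responders, and higher disease activity went with higher SUV, so the share may be higher. That stands, and step 3 shows that it changes little.

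Third, this is a declared pilot, and section 5.8 concedes that adjustment is limited by sample size. That favours balance by design, which uses no degrees of freedom until the stratum enters the model.

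A reader might infer more than the documents support:

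- *That disease activity is disregarded in forming the arms.* Matching on it is promised; what is missing is a procedure.
- *That patients without visible uptake dilute the effect and should not be enrolled.* The outcome is continuous SUV, and nothing in the documents says that these patients cannot respond. The hypothesis that "treatment with abatacept decreases and/or suppresses or prevents myocardial inflammation in RA" includes prevention, and section 5.6 builds the Aim 2 referent map from patients without uptake.
- *That CDAI of 10 or more should be an entry criterion.* Section 2.1 does say that "only the CDAI≥10 remained significantly associated with a higher SUV mean", but this concerns disease scores, race and BMI. The abatacept association also survived adjustment for disease activity. Leaving inadequate response to the treating rheumatologist is a permissible choice.

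**Conclusion.** The concern holds as a weakness in allocation and in the description of the analysis. Baseline uptake is not an allocation factor, the promised matching cannot come from alternation, and the two descriptions of the Aim 1 model differ on baseline adjustment.

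With 8 positives among 20, a split of 6:2 or worse has probability 0.17, and a 6:2 split implies a baseline gap of about 0.48 SUV units against a planned difference of 0.6. These figures assume that enrolled patients resemble the pilot cohort, that enrolment order is unrelated to uptake, and that medians can stand in for means. The 0.48 is a gap at baseline, not a bias in the result; the part reaching an unadjusted comparison depends on a scan-to-scan correlation that the documents do not give. The change is worth making because it uses a scan that already precedes allocation. It does not call for a different study population.

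**What to change.** **Sections 7.2 and 9.2.** Replace alternation with a randomly generated 1:1 list, concealed from those who enrol, in two strata: visible uptake on the baseline scan, yes or no. Use small permuted blocks. Blocks of two hold the arms to a difference of one positive patient (0.1 × 1.2 = 0.12 SUV units) but are easy to guess in an open trial. A random mix of two and four allows a difference of at most two (0.24).

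**Section 12.1 and the synopsis.** State in both places that the Aim 1 model includes baseline SUV and the uptake stratum. Withdraw the matching sentence or describe its procedure. Change by baseline uptake status may be tabulated, but only descriptively: about four positive patients per arm support no test.

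**Section 5.4.** Write down what counts as visible uptake; the section mentions visual assessment but gives no rule.

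**Cost.** An amendment, a two-stratum list, and a yes/no read by the blinded nuclear cardiologist before each allocation. No extra scan, visit or patient is needed. Incomplete blocks may leave the arms slightly unequal, for example 11:9. Section 9 starts treatment on the date of the baseline visit while section 10 allocates only after the scan, so those two statements need to be reconciled when the read is scheduled.

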# 6.2. Exclusion criteria:

- Prior biologic use other than rituximab in the past 3 months, or rituximab use in the past 6 months.
- Any prior self-reported physician diagnosed CV event (myocardial infarction; angina; stroke or Transient Ischemic Attack (TIA); heart failure; prior CV procedure (i.e., coronary artery bypass graft, angioplasty, valve replacement, pacemaker).
- Active or on-treatment cancer within 5 years of baseline visit
- Prior use of immune checkpoint inhibitors.
- Known pregnancy, HIV, hepatitis B, hepatitis C, active (or untreated latent) tuberculosis.
- Prisoners or subjects who are compulsory detained.

## 7.RECRUITMENT AND BLINDING

## 7.1. Recruitment Plan

The target population to be recruited is patients 18 years and older with a clinical diagnosis of RA who are deemed methotrexate-inadequate responders (MTX-IR) by their treating rheumatologist. Patients will be recruited from the rheumatology clinics of Columbia University Medical Center or referred from local rheumatologists. The treating rheumatologists will alert study staff when a patient is deemed a MTX-IR, prior to a switch or escalation of DMARDs. The Site Coordinator will speak with the patient to go over pre-screening inclusion/exclusion criteria, explain the trial, and assess interest.

If the patient is interested in participating, the PI or Site Coordinator must obtain informed consent prior to any screening procedures. The research protocol will be explained in detail, including all possible risks and benefits. During the consent process, the study coordinator or investigator probes the patient's understanding of the protocol. All participants will be told that the study is voluntary, that they have no obligation to participate, and that they may decline or

withdraw at any time without compromising their care. Subjects will have ample opportunity to

ask questions prior to signing the consent form. Eligible subjects will be allowed as much time as necessary to determine whether they wish to participate in the study.

# 7.2. Randomization and Blinding

Upon confirmation of subject eligibility, the Study Coordinator will determine treatment assignment through an unblinded 1:1, consecutively, alternating randomization. The nuclear cardiologist reading the FDG-PET/CT scans will be blinded to treatment assignment. Laboratory staff who run bioassays on biospecimen samples will also be blinded to treatment assignment. Subjects will be instructed NOT to discuss their treatment with the nuclear cardiologist and the staff. The nuclear cardiologist and the staff will also be instructed to remind the subject that treatment should not be discussed.

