**Accrual goal and rate.** Patient enrollment will take place over a period of 2 years from initiation of the study. With aims of enrolling 10 patients per year, the enrollment rate is estimated as 1 patient per month.

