#### 5.STUDY DESIGN AND METHODOLOGY

**5.1. Overview.** The aim of this study is to prospectively evaluate the effects on myocarditis in RA of abatacept, a CTLA4-Ig fusion protein that binds CD80/86 (B7-1/B7-2), through its effect on T cell regulation. RA patients without clinical CVD, not on recent biologic DMARDs, and with inadequate response to methotrexate (MTX), will undergo cardiac FDG PET/CT imaging at baseline to assess myocardial inflammation. RA patients will be randomized in an unblinded, 1:1 ratio to treatment with abatacept vs adalimumab. A repeat cardiac FDG PET/CT will be performed16(±2) weeks post-biologic treatment. T cell subpopulations associated with myocardial FDG uptake will be evaluated at both points in time with their transcriptional phenotype outlined by RNAseq. Conventional CVD risk factors and measures of RA disease activity will be ascertained.

**5.2. Study Population.** Patients age > 18 years, fulfilling the American College of Rheumatology 2010 classification criteria for RA (60), with inadequate response to MTX, and not on recent biologic DMARD treatment, will be recruited from the rheumatology clinics of Columbia University Medical Center and by referral from local rheumatologists. Exclusion criteria: 1) prior biologic use, other than rituximab in the past 3 months, or Rituximab use in the past 6 months; 2) any prior self-reported physician diagnosed CV event (myocardial infarction; angina; stroke or Transient Ischemic Attack (TIA); heart failure; prior CV procedure (i.e., coronary artery bypass graft, angioplasty, valve replacement, pacemaker); 3) active or on-treatment cancer within 5 years of baseline visit or prior use of immune checkpoint inhibitors; 4) Known pregnancy, HIV,

hepatitis B, hepatitis C, active (or

untreated latent) tuberculosis.

**5.3. Study visits.** Patients will be evaluated at baseline and 16 ( $\pm$ 2) weeks post-biologic treatment, with an interim safety visit at week 8 ( $\pm$ 2wks), and a final safety visit at week 20 ( $\pm$ 2).

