# 9.2. Treatment Algorithm

Figure 3.

Subjects will be randomized in an unblinded, 1:1, consecutive, alternating randomization to treatment with adalimumab 40 mg SQ every other week or abatacept 125 mg SQ weekly, each in addition to concomitant MTX. Subjects will remain on this new medication until the end of the treatment at 16 weeks.

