# 12. STATISTICAL ANALYSIS

12.1. Overview. This is a pilot study to evaluate the changes in FDG myocardial uptake postbiologic treatment of RA patients with abatacept vs adalimumab. Summary statistics for outcomes and predictor variables will be examined; with comparisons made using student t-test and Wilcoxon rank-sum test for normally and non-normally distributed continuous variables, respectively. Counts and percentages will be calculated for categorical variables and compared using the chi-square or Fisher's exact test, as appropriate. In Aim 1, using generalized estimating equations (GEE), models will be constructed to explore the association between treatment arms (abatacept vs adalimumab) and change in myocardial FDG uptake treated as a continuous variable (measured by SUV units). Similarly, linear mixed effects models will be used to define the association between T cell subpopulations and myocardial FDG uptake per treatment arm strata. Given the small sample size of the study, we will not have the power to adjust for multiple variables, but the two treatment arms will be matched for age, sex, and disease activity, and the contribution of RA-disease characteristics and traditional CVD risk factors to the variability of myocardial FDG uptake will be ascertained. All statistical calculations will be performed using SAS 9.4. In all tests, a 2-tailed  $\alpha$  of 0.05 will define statistical significance.

**12.2. Sample Size and Power Analysis.** Data on what is considered a significant change in myocardial FDG uptake in RA is not yet known. Hence, based on our preliminary data that included only 8 patients on abatacept, and as a proof of concept, for the proposed pilot

studies we will include 10 patients in the abatacept arm and compare them with 10 patients on adalimumab. Through normal approximation using the Z statistic, with a SD of 0.5 in the SUV units of myocardial FDG uptake seen in the RHYTHM study, we will have 80% power to detect an effect size of 0.6 between the groups, at an alpha level of 0.05.

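### Treatment is assigned by open-label strict alternation, so 19 of 20 assignments are known in advance; the comparison is not randomised as claimed, and the promised matching of arms has no mechanism

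*Combined protocol and SAP*

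**What the plan says.** Section 7.2 (Randomization and Blinding) says that "the Study Coordinator will determine treatment assignment through an unblinded 1:1, consecutively, alternating randomization". Section 9.2 (Treatment Algorithm) agrees: "Subjects will be randomized in an unblinded, 1:1, consecutive, alternating randomization". Section 5.1 describes the same step without mentioning alternation: "RA patients will be randomized in an unblinded, 1:1 ratio to treatment with abatacept vs adalimumab". The synopsis and sections 3.1 and 6 also call the trial randomised.

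The people and steps around assignment are as follows.

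- **Consent (section 6):** "Informed consent will be obtained by the Principal Investigator, co-investigator, or Study Coordinator".
- **Recruitment (section 7.1):** "The Site Coordinator will speak with the patient to go over pre-screening inclusion/exclusion criteria, explain the trial, and assess interest".
- **Last step before assignment (section 10):** "If nothing is found on the FDG PET/CT that would preclude the subject from randomization, the subject will be randomized into the study". No precluding findings are listed.
- **Pace:** section 6 describes a single centre recruiting twenty patients over 24 months, and the synopsis adds that "the enrollment rate is estimated as 1 patient per month".

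On comparability of the arms, section 12.1 and the synopsis say that "the two treatment arms will be matched for age, sex, and disease activity". This stands beside the statement that the sample is too small to adjust for several variables; the synopsis excepts anti-CCP status only. Neither place describes a matching, stratification or minimisation procedure.

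**The concern.** Random allocation protects a comparison because nobody who decides on entry can foresee the next assignment. Alternation removes that protection, and the open-label design makes the order visible to staff. Someone who knows the next arm can hold a patient back, approach a different one first, or judge a borderline scan differently. None of this requires bad faith.

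The scan step is the most sensitive. The baseline PET/CT supplies the baseline value of the primary outcome and is done before assignment, and the findings that would stop a patient are undefined.

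The matching statement makes matters worse, because it is the only reassurance offered alongside the limited covariate adjustment. Disease activity is not a neutral factor here. Section 2.1 reports that CDAI of 10 or more went with a 0.31 higher SUV mean and was the only one of the factors listed there to stay significant after adjustment. With 10 patients per arm, balance on it is left to entry order and staff choice.

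At stake are the validity of the between-arm test at two-sided 0.05 and the accuracy of the word randomised in any report.

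**Working it through.** **1. What the text fixes.** The total is 20 (section 6), 10 per arm (section 12.2), assigned in consecutive alternation (sections 7.2 and 9.2). The plan gives no figure for predictability, so there is none to reproduce.

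**2. Predictability under alternation.** Only 2 sequences are possible, according to which arm comes first. Given the first assignment, numbers 2 to 20 are determined: 19/20 = 95%. If the first arm is chosen at random, the expected number of correct guesses is 0.5 + 19 = 19.5 of 20. If the starting arm is also fixed in advance, which the documents do not say, it is 20 of 20.

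**3. The same count for random schemes.** For simple randomisation and blocks, the guesser always names the arm with fewer patients so far and tosses a coin at ties. For minimisation, the basis of the guess is given in the table. The blocks-of-4 figure is exact, 5 × 17/6 = 14.17. The simple figure is 20 × 0.5. The rest come from 20,000 simulated lists each.

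| Scheme | Expected correct guesses of 20 |
|---|---|
| Alternation | 19.5 |
| Permuted blocks of 4 | 14.2 |
| Permuted blocks, size 4 or 6 at random, unstratified | 13.7 |
| Minimisation, 80/20, three 50% binary factors, staff track arm totals only | 12.9 |
| Same minimisation, staff track every factor count | 14.8 |
| Simple randomisation | 10.0 |

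**4. Illustration of what steering could do.** The documents do not say how much selective entry would shift the outcome, so shifts of 0.1 and 0.2 SUV in the between-arm change are assumptions. With a two-sided Z test, 10 per arm and no true treatment effect:

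- SE = SD × √(2/10)
- False-positive rate = P(Z > 1.96 − shift/SE) + P(Z < −1.96 − shift/SE)

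Section 12.2 gives SD 0.5, so SE = 0.2236. As a second value I assume SD 0.8, from the SUV mean interquartile range of 1.5 to 2.6 in section 2.1: (2.6 − 1.5)/1.35 = 0.81 if the distribution were normal. Then SE = 0.3578.

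| SD | Shift | Shift/SE | False-positive rate |
|---|---|---|---|
| 0.5 | 0 | 0 | 5.0% |
| 0.5 | 0.1 | 0.447 | 0.0652 + 0.0080 = 7.3% |
| 0.5 | 0.2 | 0.894 | 0.1433 + 0.0022 = 14.5% |
| 0.8 | 0.1 | 0.280 | 0.0464 + 0.0126 = 5.9% |
| 0.8 | 0.2 | 0.559 | 0.0806 + 0.0059 = 8.6% |

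**5. Matching.** Alternation by order of entry uses no patient characteristic. It guarantees 10 and 10, and nothing about age, sex or disease activity. The procedure in sections 7.2 and 9.2 therefore cannot produce what section 12.1 and the synopsis promise.

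**The case against.** The best defence is that this is a 20-patient proof-of-concept pilot. The scan reader and laboratory staff are blinded, and section 5.8 says that a larger, blinded randomised trial would have to follow if the preliminary data are confirmed. That limits the consequence, but blinded reading addresses assessment, whereas selection acts before treatment begins. Section 5.8 lists the lack of blinding as a limitation and does not mention alternation.

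Several narrower objections have force.

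- **Foreknowledge at first approach is less than complete.** Consent, laboratory screening and the scan come between approach and assignment, and a patient ahead in the queue may fail screening. So 19 of 20 is exact at the moment of assignment and an upper bound when staff choose whom to approach. At about one patient a month the softening is small.
- **Baseline uptake is partly handled.** The synopsis says the GEE models take baseline uptake into account; section 12.1 omits the phrase. Adjustment for baseline does not remove selection on other characteristics.
- **The false-positive figures are only illustrative.** The shifts are assumed. The SD of 0.8 comes from cross-sectional, skewed values rather than from change, and the planned model is GEE rather than a Z test. To bias change, staff would have to favour patients likely to improve. The verdict does not rest on these figures.
- **The CONSORT diagram and Figure 3 are not visible in the text reviewed.** They are unlikely to override a method stated in two sections.
- **The undefined scan findings are a separate gap.** They would need attention under any allocation scheme, but foreknowledge makes them matter more.

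**Conclusion.** The concern holds and must be fixed. Allocation as written is deterministic and open, 19 of 20 assignments are known from the one before, and the description of the trial as randomised is not supported. The matching statement has no described mechanism, and alternation cannot supply one. These conclusions follow from the text and need no assumption beyond the first arm not being fixed in advance; if it is, the count is 20 of 20.

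The direction and size of any bias are unknown. Under the assumed shifts of 0.1 to 0.2 SUV, the nominal 5% error rate would be between 5.9% and 14.5%, depending on the shift and the SD. Pilot status limits how much rests on the result, but selection at entry cannot be repaired in an analysis of 20 patients.

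**What to change.** 1. In sections 7.2 and 9.2, replace alternation with a computer-generated random sequence. Either minimisation with a random element (for example 80/20) on age group, sex and CDAI category, or permuted blocks of randomly varying size stratified by CDAI category, would suit. A concealed unstratified list would also cure the main defect, but would balance none of the named factors.
2. Conceal the sequence from everyone who screens or consents, through an electronic module or a list held by a team member outside enrolment.
3. Assignment already follows eligibility and the baseline scan. Add that it is released only once both decisions are irrevocably recorded, and state in section 10 which scan findings preclude randomisation.
4. In section 12.1 and the synopsis, replace the matching statement with the factors actually balanced. Stratifying on CDAI alone would not support a claim about age and sex. Restore in section 12.1 the synopsis wording on baseline uptake, and adjust for no more than baseline SUV and CDAI category at this sample size.
5. If patients have already been assigned by alternation, describe the comparison as non-randomised.

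The cost is a short amendment to sections 7.2, 9.2, 10 and 12.1 and the synopsis, plus the module or list. No extra patients, visits or hired staff are needed. There are two drawbacks. In an open-label trial of this size the next arm stays partly guessable, about 13 to 15 of 20 against 19.5 now. The split may also not be exactly 10 and 10: with blocks of 4 or 6 in two equally common CDAI strata, simulation gives an exact split in about 55% of lists.
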